This will be a prospective, cluster-randomized trial comparing two methods of induction of labor at term among women who present for delivery at Parkland Hospital. Eligible participants will include nulliparous and multiparous women at 37 weeks gestation or greater, with a living, singleton fetus and no major fetal malformations, in cephalic presentation, with intact membranes, no prior uterine scar, who qualify for prostaglandin administration and who have a cervical dilation of 2 centimeters or less, measured at the level of the internal os. Patients with non-reassuring fetal status, HIV, active herpes outbreak, a prior uterine scar, or any contraindication to prostaglandins (including 4 or more painful contractions per 10 minutes prior to prostaglandin administration) will be excluded from participation in the study. Computer-generated cluster randomization will occur on a weekly basis for all study participants, to either the combination method of foley bulb plus oral misoprostol regimen (study group/standard of care plus foley bulb) or to oral misoprostol alone regimen (control/standard of care).

According to the randomization protocol each week, participants will be randomized to either the standard of care (oral misoprostol/control group) or standard of care plus foley bulb (study group). The study group will undergo placement of a 30 French foley catheter filled with 30-35cc sterile saline into the cervix in addition to the standard regimen of oral misoprostol 100 micrograms given every 4 hours for a maximum of 2 doses, for patients who meet criteria for fetal well-being, and do not had more than 4 painful contractions in 10 minutes. Misoprostol will not be administered to patients who have progressed to active labor, defined as 4 centimeters cervical dilation. The control group will undergo induction with the standard of care misoprostol protocol alone.

[name]

Induction of labor with oral miso versus combined oral miso plus foley: a Cluster randomized trial

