Management of labor will proceed according to the standard induction protocols in place at Parkland Hospital. The number of misoprostol doses (up to 2 doses for a single induction event) will be recorded. The need for oxytocin following misoprostol will be determined according to routine obstetric management currently used at Parkland Hospital. All women meeting inclusion criteria as described above who require induction of labor will be included in the study. According to the cluster randomization protocol, either a combination method of standard of care plus foley bulb, or standard of care (oral misoprostol) alone will be implemented each week on the Labor and Delivery unit. During weeks randomized to the standard of care plus foley bulb, all eligible women undergoing induction of labor will receive prostaglandin using the current labor stimulation regimen as well as transcervical placement of a 30 French foley catheter with a 30cc balloon, filled with 30 to 35 cc of 0.9% sodium chloride solution, according to FDA guidelines for filling the foley bulb. Induction start time and foley bulb placement time will be recorded. Success of foley bulb placement and time to successful placement will be recorded. Complications of induction will be recorded, such as vaginal bleeding, fetal distress, rupture of membranes, or emergent delivery within 30 minutes of foley bulb placement. Failed foley bulb placement will be determined ultimately by the faculty on Labor and Delivery as per management practices. Analgesia requirement during labor will be recorded. Transcervical foley bulb will remain in place until expelled spontaneously, or for up to 12 hours during induction. The need for removal of foley bulb prior to being

[name]

Induction of labor with oral miso versus combined oral miso plus foley: a Cluster randomized trial

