In summary, the research team will not have direct contact with the patient. All information will be obtained either using the Obstetric database or data entry forms with information obtained from the electronic medical record. These indices are routinely recorded by labor and delivery unit staff for labor induction (eg. Time of misoprostol given, etc.).

Recruitment methods and consenting process:

All subjects will be women who deliver at Parkland Health and Hospital System. The cluster randomized trial design is such that each week, the chosen method of induction of labor in patients meeting inclusion criteria is randomized to either standard of care (oral misoprostol) or standard of care plus foley bulb. The weekly cluster randomization method is chosen because randomizing on an individualized basis would create risk on a busy labor and delivery unit where nurses administer medications to more than one patient during a shift. All patients who would meet criteria for induction of labor will be participants in the study. A waiver of consent will be requested for this study, as the two methods of induction being compared are both widely accepted and practiced methods used for women with an unfavorable cervix who require induction of labor. The risks and benefits of induction of labor will be discussed with each patient prior to

[name]

Induction of labor with oral miso versus combined oral miso plus foley: a Cluster randomized trial

administration and consent for delivery obtained, consistent with the current standard of care on Labor and Delivery at Parkland Hospital. Patients will be fully informed about the agents used for induction of labor (i.e., misoprostol alone or foley bulb and misoprostol, as well as oxytocin) and verbal consent as standard of care for induction will be obtained. The risk of transcervical foley bulb is minimal, and the primary risk of participation in the study is breach of confidentiality. The waiver of consent is appropriate because all patients will receive the same standard of care, and all methods of induction utilized are approved by the American College of Obstetricians and Gynecologists. Furthermore, obtaining consent from individual patients is impractical on a busy labor and delivery unit that would require research staffing for 24 hours a day, 7 days per week.

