With the increasing frequency of cesarean delivery and the increasing morbidity of multiple cesarean deliveries, a successful vaginal delivery in a woman whose only alternative is cesarean delivery has the potential to improve quality of life, save cost in hospitalization days, wound complications, and improve the chance for subsequent

[name]

Induction of labor with oral miso versus combined oral miso plus foley: a Cluster randomized trial

vaginal delivery, compounding the savings during a woman's lifetime. If the study shows no improvement in vaginal delivery rates or increased adverse outcomes in the study group, the study may prevent healthcare providers from utilizing an induction method which has little potential benefit other than convenience to the provider.

Biostatistics:

The current vaginal delivery rate at Parkland Hospital among women undergoing induction of labor is 76%, which has been consistent for at least the past 4 years (internal data). This study will be conducted as a superiority trial with analysis performed as intent to treat. To detect a 5% increase in vaginal delivery from 76% to 81% with a power of 80% and a type I error of 5%, a sample size of 2118 is required, with 1059 women in each group with comparisons using the Pearson chi-squared test. A planned interim analysis by the Data Safety Monitoring Board take place at 50% recruitment. In order to preserve the overall type I error rate of 0.05 we will apply the Lan-DeMets spending function with the O'Brien-Fleming type boundaries. This reduces the ultimate significance level of the trial through the completion of the trial from 0.05 to 0.049 and alters the sample size to 1065 women in each arm or 2130 total. A ten percent dropout rate still requires approximately 2500 participants to be screened ($2130/0.90 = 2367$).

In 2015 at Parkland Hospital, approximately 885 women at term (greater or equal to 37 weeks gestation) with cervical dilation equal to or less than 2cm received at least one dose of oral misoprostol for induction of labor. Based on these frequencies, recruitment will take approximately 2.5 years to achieve the study goal of 2130 women who meet inclusion criteria. Statistical analysis will be performed using SAS 9.3 and include Student's t-test, Wilcoxon rank-sum test, Pearson chi-squared test, and logistic

[name]

Induction of labor with oral miso versus combined oral miso plus foley: a Cluster randomized trial

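### Whole weeks are randomized, but the sample size and the planned tests treat women as individually randomized, so the stated 80% power and 5% type I error do not hold

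*Combined protocol and SAP*

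**What the plan says.** The design is clustered by calendar week at one hospital. Under Concise Summary of Project, "Computer-generated cluster randomization will occur on a weekly basis for all study participants". Study Procedures says that one of the two methods "will be implemented each week on the Labor and Delivery unit". Under Recruitment methods and consenting process, "each week, the chosen method of induction of labor in patients meeting inclusion criteria is randomized".

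The Biostatistics section plans for a rise in vaginal delivery from 76% to 81% with 80% power and 5% type I error, and concludes that "a sample size of 2118 is required, with 1059 women in each group with comparisons using the Pearson chi-squared test". It then provides for one interim look: "A planned interim analysis by the Data Safety Monitoring Board take place at 50% recruitment". With a Lan-DeMets spending function and O'Brien-Fleming type boundaries, the final level becomes 0.049 and the sample size 1065 per arm, 2130 in total. The only other allowance is for 10% dropout. The methods listed are Student's t-test, "Wilcoxon rank-sum test, Pearson chi-squared test, and logistic" regression, plus an analysis of the primary outcome stratified by parity.

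The document gives no ICC, design effect, cluster size or number of weeks per arm, and names no method that accounts for week.

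**The concern.** When a whole week is assigned to one arm, the arms differ by chance in which weeks they received as well as in which women. If the vaginal delivery rate varies at all between weeks for reasons unrelated to treatment, such as who is on duty or how busy the unit is, outcomes within a week are correlated. A chi-squared test on women ignores that source of variation. Its standard error is too small, its confidence interval too narrow, and it rejects too often.

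There are two separate consequences. The planned unadjusted test exceeds its 5% type I error. A test that respects the randomized unit keeps its level but has less than 80% power with 2130 women. The interim look matters too. Under Subject Data and Safety Monitoring it can stop the trial for harm, or lead to early termination for benefit, and a boundary applied to an unadjusted statistic is easier to cross than intended.

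**Working it through.** **Inputs from the Biostatistics section.** Rates 76% and 81%; power 80%; type I error 5% (sidedness not stated); one look at 50% recruitment; final level 0.049; 1065 per arm; 885 eligible women per year. **Assumed:** the ICC, which the documents do not give, from 0.001 to 0.05, and equal weekly numbers.

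**Step 1: reproduce the stated sample size.** The pooled two-proportion formula is

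n per arm = [z(1−α/2)·√(2·p̄·q̄) + z(0.80)·√(p₁q₁ + p₂q₂)]² / (p₂ − p₁)²

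with p̄ = 0.785, √(2 × 0.785 × 0.215) = 0.5810 and √(0.1824 + 0.1539) = 0.5799.

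- α = 0.05, two-sided: (1.9600 × 0.5810 + 0.8416 × 0.5799)² / 0.0025 = 1058.6, which rounds up to the stated 1059.
- α = 0.049: using 1.9686 gives 1065.1, against the stated 1065.
- A one-sided test would give 834 and a continuity correction 1099, so neither was used.

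The Lan-DeMets O'Brien-Fleming boundary at half the information is z = 2.963 (p = 0.0031) at the interim and z = 1.969 (p = 0.0490) at the end, matching the plan. Its figures are therefore those of an individually randomized trial, with a design effect of exactly 1.

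**Step 2: cluster size.** m = 885/52 = 17.0 women per week, and 2130/17.02 ≈ 125 weeks.

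**Step 3: effect of clustering.**

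- Design effect: DE = 1 + (m − 1) × ICC.
- Valid power: the Step 1 formula solved for power at α = 0.049, with 1065/DE women per arm.
- Type I error of an unadjusted look: 2 × [1 − Φ(critical z / √DE)].
- Overall type I error: probability of crossing either boundary, from the bivariate normal distribution with correlation √0.5.

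For ICC 0.01, DE = 1 + 16.02 × 0.01 = 1.160. The effective size is 1065/1.160 = 918 per arm, and the valid power is 73.9%. The final-look error is 2 × [1 − Φ(1.9686/1.077)] = 6.8%, and the interim error is 2 × [1 − Φ(2.963/1.077)] = 0.60% instead of 0.31%.

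| Assumed ICC | DE | Valid power, 2130 women | Unadjusted error, interim | Unadjusted error, final | Unadjusted error, overall | Women analyzed for 80% power (2130 × DE) |
|---|---|---|---|---|---|---|
| 0 | 1.00 | 80.0% | 0.31% | 4.9% | 5.0% | 2130 |
| 0.001 | 1.02 | 79.4% | 0.33% | 5.1% | 5.2% | 2165 |
| 0.005 | 1.08 | 76.9% | 0.44% | 5.8% | 6.0% | 2301 |
| 0.01 | 1.16 | 73.9% | 0.60% | 6.8% | 7.0% | 2472 |
| 0.02 | 1.32 | 68.3% | 0.99% | 8.7% | 9.0% | 2813 |
| 0.05 | 1.80 | 55.0% | 2.73% | 14.2% | 15.1% | 3837 |

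**Step 4: simulation.** Beta-binomial data were simulated for 126 weeks of 17 women, 20,000 replicates, testing at 0.049. At ICC 0.01 the unadjusted test rejected 6.9% of the time under the null. A t-test on weekly proportions rejected 4.9% under the null and had 73.6% power. At ICC 0.005, 0.02 and 0.05 the unadjusted test rejected 5.7%, 8.5% and 14.4% under the null. These agree with the formulas.

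**The case against.** The omission is not in dispute, but its size depends on an ICC nobody has stated. At 0.001 the loss is trivial. The upper end of the range looks unlikely: the between-week standard deviation implied by an ICC is √(ICC × 0.76 × 0.24), about 1.4 percentage points at 0.001, 4.3 at 0.01, 6.0 at 0.02 and 9.5 at 0.05. Nothing in the documents supports swings of 9.5 points at a single hospital with standard protocols. That is a fair reason to give the last row little weight. The 76% rate described as stable over at least four years does not settle the matter, because a stable long-run rate is compatible with variation from week to week. The reasons for correlation are also inference: the protocol mentions faculty discretion but no weekly rota.

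The listed methods could be used correctly. A t-test or Wilcoxon test can be applied to weekly proportions, and logistic regression can include week. The plan does not say so, however, and it names the Pearson chi-squared test on 1059 women per group for the comparison. It does not name the interim statistic, so the interim figures assume the same unadjusted test.

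The target of about 2500 women might give some headroom. If 2250 are analyzed (2500 × 0.9), that covers a design effect of 2250/2130 = 1.056, an ICC of about 0.0035. If all 2500 are analyzed, it covers 1.174, an ICC of about 0.011. That margin was set for dropout, and more women would not correct the unadjusted test's type I error.

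Finally, the two failures belong to different analyses. At ICC 0.01 the unadjusted test still has simulated power of about 78.5%, but at an invalid level.

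**Conclusion.** The concern holds. The plan randomizes weeks and both sizes and tests the trial as if it randomized women. Its 80% power and 5% type I error are correct only if the between-week ICC is exactly zero, which the plan neither states nor justifies. For any positive ICC the named test gives standard errors that are too small.

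Over assumed ICCs from 0.001 to 0.02, overall type I error of the unadjusted procedure runs from 5.2% to 9.0%, and power of a valid test on 2130 women from 79.4% to 68.3%. The figures assume 17 women every week; variable weekly numbers would raise the design effect. For scale, the plan lowers its final level by 0.001 to protect the overall 0.05. Ignoring clustering gives up more than that even at an ICC of 0.001 (5.2% against 5.0%). The correction should be made before any comparative analysis.

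**What to change.** - **Primary outcome, interim and final.** Name one method that takes the week as the randomized unit: logistic GEE with week as cluster and robust standard errors, logistic regression with a random week effect, or a comparison of weekly proportions. Apply the Lan-DeMets boundaries to that statistic.
- **Secondary outcomes and the parity-stratified analysis.** Account for week in the same way.
- **Planning paragraph.** State the expected number of weeks and women per week, estimate the ICC from the department's own weekly delivery data, apply 1 + (m − 1) × ICC, and report the power that 2130 women give.

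The cost is SAP wording, a small change to the SAS code and a lower stated power. No extra women are needed if that power is accepted. Restoring 80% would need about 2472 analyzed women at an ICC of 0.01, or 2472/885 ≈ 2.8 years of recruitment at the 2015 rate against 2130/885 ≈ 2.4 years.
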